One of the leading extra-hepatic causes of liver steatosis is metabolic syndrome (MS). Although, multiple definitions of MS exists; the essential components of MS include insulin resistance, increased levels of stress hormones, such as cortisol, and visceral obesity. In the obese population, the hallmarks of a metabolic syndrome are highly prevalent, being peripheral insulin resistance and increase levels of stress hormones the leading causes of organ injury. In such individuals higher levels of cortisol are expected, secondary to an over activated hypothalamic-pituitary-adrenal (HPA) (13, 14). A linear correlation between adrenal gland volume and metabolic syndrome has been demonstrated, with increased adrenal volume in patients under a metabolic syndrome status. However, once these patients are engaged on a treatment regime, leading to weight loss and diminished insulin resistance, the increase in adrenal volume tends to be reversible. Adrenal volume measurements can be achieved using cross-sectional imaging and semi-automated softwares. In clinical practice, adrenal gland dimensions are generally assessed using limb linear measurements on multidetector row computed tomography or magnetic resonance imaging (15,16).

We conducted a prospective longitudinal clinical study to correlate the effects of a very low-calorie-ketogenic diet (PRONOKAL method*), body weight loss and visceral fat reduction, with liver fat fraction, using a new MRI model of fat liver quantification (Ideal IQ**). Additionally, the degree of liver fat and its evolution, during the diet program, will be correlated with liver stiffness using MR Elastography. Adrenal gland measurements will also be made using the linear technique described by Carsin-Vu A. (16) to address its correlation with weight loss, visceral fat and liver steatosis.

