9 STUDY PROCEDURES AND OUTCOME MEASURES

9.1 Outcome measures

9.1.1 *Primary variables*

- Liver fatty infiltration, measured by a MRI technique of fat liver quantification (Ideal IQ**).
- Visceral fat, measured by the area in squared centimeters at the level of the 3rd vertebrae, using MRI technique.

9.1.2 *Secondary variable*

- Liver stiffness detected by MR Elastography
- Adrenal gland linear measurement
- Body weight
- Salivary cortisol levels

9.1.3 *End points*

- Reduction of fat infiltration into the liver between the baseline visit and 2 months (or end of the ketosis stage) and between the baseline visit and the control visit at month 6 of treatment.
- Visceral fat reduction between the baseline visit and 2 months (or end of the ketosis stage) and between the baseline visit and the control visit at month 6 of treatment.
- Correlation between degree of liver fat infiltration and liver stiffness
- Correlation between adrenal gland size and BMI, visceral fat and liver steatosis.
- Correlation between salivary cortisol levels and BMI, visceral fat and liver steatosis.
- Weight loss between the baseline visit and 2 months (or end of the ketosis stage) and between the baseline visit and the control visit at month 6 of treatment.

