Control visit at month 2 or at the end of the ketogenic stage: For patients in the VLCK diet group, as soon as the patient loses 80% of the excess weight or within 2 months of treatment, just before moving to phase 3, the patient will undergo a new control. In the case of the control group, this visit will take place at month 2 of the hypocaloric diet.

The patient will undergo a new MRI and MR Elastography. The salivary cortisol levels will also be tested. Anthropometric data are recorded, the patient undergoes a complete blood test including liver function (GOT, GPT, GammaGT, bilirubin, albumin, prothrombin time, ferritin, alkaline phosphatase) and the potential occurrence of adverse effects will be recorded.

Visit at month 6 At month 6 of the study, a new control will be performed, evaluating hepatic steatosis and visceral fat using MRI and liver stiffness using MR Elastography. The salivary cortisol levels will also be tested. A complete blood test including liver function (GOT, GPT, GammaGT, bilirubin, albumin, prothrombin time, ferritin, alkaline phosphatase) will be required and the anthropometric data, the treatment phase, the blood test results and the potential occurrence of adverse effects will be recorded.

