10.2 Analysis of objectives

For the analysis of the primary objective and the secondary objectives, the differences between visits and between groups will be studied for the changes in the ratio between liver fat and the degree of steatosis (measured by MRI), changes in the degree of liver stiffness, changes in cortisol levels in saliva, weight changes, BMI and waist circumference, and changes in the amount of visceral fat among visits. The qualitative variables will be compared using Fisher's exact test, and the quantitative variables will be compared by means of the Student's t test for paired data. If the conditions to apply the Student's t test are not met, we will use the non-parametric Mann-Whitney U test. In the case of comparing paired data, we will use the tests described above, in their version for comparing this type of data.

The Pearson correlation coefficient or Spearman's correlation coefficient if the application conditions are not met will be used to study the following: the association between reduction of hepatic steatosis and weight loss and loss of visceral fat; the association between hepatic steatosis and liver stiffness; and the association between adrenal gland size and salivary cortisol levels with weight changes, BMI, hepatic steatosis and visceral fat.

For all tests, the significance level will be set at $p < 0.05$.

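### The correlations in section 10.2 take no account of treatment arm, so a coefficient of changes over all patients can mix the difference between diets with the patient-level relation

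*Combined protocol and SAP*

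**What the plan says.** The second paragraph of section 10.2 names Pearson coefficients, or Spearman if the conditions for Pearson fail, for three sets of associations:

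- changes: "the association between reduction of hepatic steatosis and weight loss and loss of visceral fat";
- levels: "the association between hepatic steatosis and liver stiffness";
- a mixture of both: "the association between adrenal gland size and salivary cortisol levels with weight changes, BMI, hepatic steatosis and visceral fat".

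The section closes with "For all tests, the significance level will be set at" 0.05. It does not say whether a coefficient is computed over all patients, within each arm, or adjusted for arm. The comparison between visits and between groups in its first paragraph concerns changes in the outcomes, not the correlations.

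Section 9.1.3 lists some of these correlations as end points, for example "Correlation between degree of liver fat infiltration and liver stiffness" and "Correlation between adrenal gland size and BMI, visceral fat and liver steatosis", again without mention of arm. The correlation of steatosis reduction with weight loss is not on that list. It does bear on the primary aim in section 5.1, which is worded as the effects of weight loss.

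Post-baseline data are clearly intended for at least some coefficients. Section 4 says that "the degree of liver fat and its evolution, during the diet program, will be correlated with liver stiffness", and section 9.2.1 repeats the measurements after baseline, with the month 6 visit "evaluating hepatic steatosis and visceral fat using MRI and liver stiffness using MR Elastography". Section 4 also reports that the ketogenic programme produced more weight loss than a standard low-calorie diet, and that weight loss improves fatty liver.

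**The concern.** In a two-arm trial, a correlation over all patients has two sources. One is the relation among patients on the same diet. The other is the gap between the arm means, which contributes whenever both variables differ by arm. Section 4 gives reason to expect such a gap for weight loss and for liver fat reduction.

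A significant coefficient could then be read as showing that patients who lose more weight lose more liver fat, when part of it reflects only which diet each patient followed. What is at stake is the meaning of the coefficient. If both variables differ by arm, the pooled correlation really is non-zero, so the test is not invalid; it answers a different question from the one a reader is likely to have in mind.

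**Working it through.** **Inputs from the documents.** 40 patients, 20 per arm, 1:1 (sections 6.2 and 7.4); significance level 0.05 (section 10.2). The documents give no SD, no expected difference between diets and no expected correlation, so there is no figure of the plan's own to reproduce.

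**Assumptions.** Within-arm correlation r; arm differences d1 (weight loss) and d2 (liver fat reduction) in within-arm SDs; bivariate normal data; two-sided tests, since section 10.2 gives the level but not the sidedness.

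**Formula.** With equal arms, the population pooled correlation is

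pooled r = (r + d1·d2/4) / sqrt[(1 + d1²/4)(1 + d2²/4)].

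**Case A: both variables differ by the same amount, whatever r is.** At d1 = d2 = 1 the denominator is 1.25.

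- r = 0: 0.25/1.25 = 0.20
- r = 0.2: 0.45/1.25 = 0.36
- r = 0.4: 0.65/1.25 = 0.52

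At d1 = d2 = 0.5 the same three values of r give 0.06, 0.25 and 0.44. At d1 = d2 = 1.5 they give 0.36, 0.49 and 0.62.

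**Case B: the diet acts on liver fat only through weight loss.** Then d2 = r·d1. At d1 = 1:

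- r = 0: d2 = 0, pooled r = 0
- r = 0.2: d2 = 0.2, (0.2 + 0.05)/sqrt(1.25 × 1.01) = 0.22
- r = 0.4: d2 = 0.4, (0.4 + 0.10)/sqrt(1.25 × 1.04) = 0.44

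At d1 = 1.5, r = 0.4 gives d2 = 0.6 and (0.4 + 0.225)/sqrt(1.5625 × 1.09) = 0.48.

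**Case C: only one variable differs (d1 = 1, d2 = 0).** Pooling slightly lowers the coefficient: 0.4/sqrt(1.25) = 0.36.

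**Share of trials significant.** 40,000 simulated trials per setting, 20 v 20. The adjusted coefficient is the correlation of arm-centred values, with 40 − 3 = 37 degrees of freedom.

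| r | d1/d2 | pooled | arm-adjusted |
|---|---|---|---|
| 0 | 0.5/0.5 | 6% | 5% |
| 0 | 1/1 | 24% | 5% |
| 0 | 1.5/1.5 | 67% | 5% |
| 0 | 1/0 | 5% | 5% |
| 0.4 | 1/1 | 95% | 73% |
| 0.4 | 1/0 | 64% | 73% |

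The row with r = 0 and 1/0 is also Case B at r = 0.

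**Follow-up levels.** A month 2 or month 6 level carries baseline spread as well as change. If the changes differ by 1/1 SD and the baseline SD is k times the SD of change, independent of it, the levels differ by 1/sqrt(1 + k²) SD: 0.71 for k = 1 and 0.45 for k = 2. At r = 0 the pooled test is then significant in 11% and 6% of trials, so levels are less affected than changes.

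**Precision.** Fisher z for an observed r of 0.4, with atanh(0.4) = 0.424:

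- one arm of 20, SE 1/sqrt(17): 95% CI −0.05 to 0.72
- arm-adjusted with 40 patients, SE 1/sqrt(36): 95% CI 0.10 to 0.64

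**The case against.** The strongest reply is that the protocol itself describes weight loss as what changes liver fat. Under that account Case B applies, and pooling barely matters: 0.2 becomes 0.22, 0.4 becomes 0.44, and nothing appears where there was no relation. To turn 0.2 into 0.36 at d1 = 1, the diet would have to move liver fat by 1 − 0.2 = 0.8 SD by some other route, and no section states such an effect. This stands as a limit on size. It does not remove the point, because the documents do not rule out a diet effect beyond weight loss, and the trial is the place where that would be learned.

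A reader might go further than the documents allow in four ways.

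- **Pooling as an error that gives 24% or 67% false positives.** Those rates need large arm differences in both variables and no within-arm relation at all, which fits poorly with section 4. They are upper-end cases, and the pooled correlation they detect is real.
- **Visit or interval missing for every correlation.** Section 9.1.3 gives both change intervals for liver fat, visceral fat and weight. Only the level-on-level correlations lack a visit, and that is missing detail.
- **The listed correlation end points as shown to be distorted.** For stiffness, adrenal size and cortisol the documents give no figure for any effect of diet. Without one, the mechanism does not operate.
- **The trial's main comparison as compromised.** The randomized comparison of the diets uses no correlation. Baseline correlations precede treatment, so any arm difference there is due to chance.

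Finally, adjustment discards between-arm variation, which is real signal if weight loss carries the diet effect. That is a good reason to keep the pooled value, though not to report it alone.

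**Conclusion.** The point holds in a conditional form. Section 10.2 specifies simple coefficients with no account of arm, and no other section supplies one. For correlations of changes, above all steatosis reduction with weight loss and with visceral fat loss, a coefficient over all patients can combine the difference between diets with the patient-level relation.

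The size in this trial is unknown. Under assumed differences of 1 SD in both variables the inflation is appreciable; if the diet works on liver fat only through weight loss it is negligible. Follow-up levels are less exposed than changes. The issue is one of interpretation in supporting and secondary analyses of a study that section 7.5 calls an exploratory pilot. It is a cheap improvement, not a defect that threatens the trial's conclusions about the diets.

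**What to change.** In section 10.2, for every correlation that uses changes or month 2 or month 6 levels:

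1. Report the arm-adjusted coefficient (partial Pearson or partial Spearman) with its 95% CI beside the pooled one.
2. Base any statement about patients, including those drawn from the correlation end points in section 9.1.3, on the arm-adjusted coefficient.
3. Keep the pooled value, with a note that it includes between-arm variation.
4. Treat per-arm coefficients as optional and descriptive, since they are imprecise at 20 patients.

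The cost is SAP wording, one degree of freedom and one extra column; no new data are needed. Section 10.2 names 11 pairs of variables (2 for steatosis reduction, 1 for stiffness, and 2 × 4 = 8 for adrenal size and cortisol). Over two intervals or two post-baseline visits the column adds 11 × 2 = 22 coefficients.

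Fewer results will be significant when both variables differ by arm: 73% against 95% at an assumed within-arm r of 0.4 and differences of 1/1 SD. When only one variable differs, adjustment helps: 73% against 64%.

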5.2 Secondary aims

- To correlate the degree of liver fat infiltration and liver stiffness using MR Elastography
- To investigate the hypothesis of a linear correlation between adrenal gland size and variables commonly associated to insulin resistance such as BMI, visceral fat and liver steatosis.

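### Section 10.2 compares mean changes but plans no correlation of change in stiffness with change in liver fat, and sets adrenal size and cortisol levels against weight change at an unnamed visit

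*Combined protocol and SAP*

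**What the plan says.** Section 4 sets the task as: "the degree of liver fat and its evolution, during the diet program, will be correlated with liver stiffness using MR Elastography". It also says adrenal measurements will be related to weight loss, visceral fat and steatosis.

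The formal statements are narrower. The secondary aim in 5.2 is "To correlate the degree of liver fat infiltration and liver stiffness using MR Elastography", and the end point in 9.1.3 is "Correlation between degree of liver fat infiltration and liver stiffness". The adrenal and cortisol end points in 9.1.3 are likewise levels against BMI, visceral fat and steatosis. Weight change is not in those lists.

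Section 10.2 lists three groups of correlations:

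- "the association between reduction of hepatic steatosis and weight loss and loss of visceral fat": change with change.
- "the association between hepatic steatosis and liver stiffness": no change term and no visit.
- "the association between adrenal gland size and salivary cortisol levels with weight changes, BMI, hepatic steatosis and visceral fat": adrenal size and cortisol as levels, weight as a change, and no visit.

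Its first paragraph separately plans comparisons between visits and between groups of "changes in the degree of liver stiffness, changes in cortisol levels in saliva, weight changes, BMI and waist circumference".

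**The concern.** The part of Section 4 about the evolution of liver fat has no end point in 9.1.3 and no method in 10.2. Shorthand is a less likely explanation because the same sentence of 10.2 uses change wording for steatosis, weight and visceral fat.

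A level correlation mainly compares different patients. It can be strong when stiffness does not move with liver fat during the diet, and weak when it does. A level set against a change mixes a between-patient quantity with a within-patient one, and its meaning depends on which visit supplies the level. The risk is that a significant cross-sectional coefficient is reported as evidence that stiffness tracks liver fat during weight loss, or that a real link between cortisol or adrenal size and weight loss is missed.

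**Working it through.** **Inputs from the documents.** 40 patients, 20 per arm (7.4). Significance level 0.05 (10.2); sidedness is not stated, so two-sided is assumed. MRI, elastography and salivary cortisol at onset, month 2 and month 6 (9.2.2). There is no planned figure to reproduce: 7.5 gives no effect size, SD or power. Every correlation below is an assumption. The percentages come from simulations of 20,000 runs per scenario.

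**1. Level with level (liver fat and stiffness).** Let baseline levels correlate at r_b and changes at r_c, with changes independent of baseline, and let each variable correlate ρ between visits. With baseline variance 1, the change variance is 1/ρ² − 1 and the follow-up variance is 1/ρ². Then

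follow-up level correlation = r_b·ρ² + r_c·(1 − ρ²).

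| Scenario | Quantity | ρ = 0.5 | ρ = 0.7 | ρ = 0.9 |
|---|---|---|---|---|
| r_b = 0.5, r_c = 0 | follow-up level r | 0.125 | 0.245 | 0.405 |
| | significant | 12% | 34% | 76% |
| r_b = 0, r_c = 0.5 | follow-up level r | 0.375 | 0.255 | 0.095 |
| | significant | 68% | 36% | 9% |

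In the first scenario the baseline level correlation is significant in 92% of runs and the change correlation in about 5%. In the second, the baseline level correlation is significant in about 5% and the change correlation in about 92%.

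A different model gives the same message. Suppose 60% of the variance in each variable is stable between patients.

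- Stable parts correlate 0.6, changes unrelated: level r = 0.6 × 0.6 = 0.36, significant in 64%; change r = 0, significant in 5%.
- Stable parts unrelated, changes correlate 0.5: level r = 0.4 × 0.5 = 0.20, significant in 24%; change r = 0.50, significant in 92%.

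**2. Level with change (cortisol or adrenal size against weight change).** Under the first model, with r_c = 0.5:

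- Baseline level against weight change: expected r = 0, significant in about 5%. This follows directly from taking baseline as independent of change.
- Follow-up level against weight change: r = r_c·√(1 − ρ²) = 0.5 × 0.866 = 0.43, 0.5 × 0.714 = 0.36, 0.5 × 0.436 = 0.22 for ρ = 0.5, 0.7, 0.9. The simulated means are 0.43, 0.35 and 0.21, significant in 81%, 63% and 27%.
- Adjusting follow-up for baseline multiplies the correlation by 1/√(1 − ρ²): 1.15 at ρ = 0.5 and 1.40 at ρ = 0.7.

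**3. Need for arm adjustment.** The diets are expected to differ in effect, so pooling the arms can itself create a change correlation. If the arms differ by d within-arm SDs in both changes and there is no link within arms, the pooled r is (d²/4)/(1 + d²/4).

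- d = 1: 0.25/1.25 = 0.20, significant in 24% of runs.
- d = 1.5: 0.5625/1.5625 = 0.36 (simulated mean 0.37), significant in 67%.
- With arm adjustment: 0.00, significant in 5%.

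**4. What 40 patients can show.** The smallest correlation detectable with 80% power is tanh((1.960 + 0.842)/√(n − 3)): 0.43 for n = 40, 0.49 for 30 completers (assumed) and 0.59 for one arm of 20. Adjusting for arm at n = 40 uses √36 and gives tanh(0.467) = 0.44. An observed arm-adjusted r of 0.50 would have a 95% CI of tanh(0.549 ± 1.960/6), which is 0.22 to 0.70.

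**The case against.** The case for leaving the text alone has real weight.

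- **10.2 matches the formal aims.** Sections 5.2 and 9.1.3 are worded as levels, and the change question for stiffness rests on one sentence of the rationale. That sentence does not say change in stiffness. This stands: the level correlations are legitimate and can stay. The rationale still announces an analysis of evolution for which the plan has no method.
- **No aim or end point asks whether change in cortisol follows weight change.** This stands too. A reader might infer that a change-with-change cortisol analysis was promised; it was not. But 10.2 itself brings in weight changes, and Section 4 links adrenal size to weight loss, so the pairing needs a defined meaning.
- **Mean changes are analysed.** A reader might infer that the plan cannot show whether stiffness or cortisol falls as fat and weight fall. The first paragraph of 10.2 rules that out, since average falls would be visible by visit and by arm. Only the patient-level association is absent.
- **The wording may be loose.** Salivary cortisol levels is also the name of the variable, so 10.2 may intend changes throughout. If so, a clarification is still needed, because the text read literally gives a different coefficient.
- **The magnitudes are hypothetical.** They are, and they move widely with ρ. They show that the two analyses can disagree, not by how much they will here.

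**Conclusion.** The point holds in limited form. As written, these correlations cannot show whether patients who lose more liver fat or weight have larger falls in stiffness, adrenal size or cortisol. For stiffness, the plan omits an analysis that its rationale announces. For adrenal size and cortisol, it pairs a level with a change at an unspecified visit.

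Under the assumed inputs, level and change analyses can give opposite answers (92% against about 5% significant, in either direction, when baseline levels are used). The level-with-change pairing loses between little and nearly all of the power, depending on the visit chosen and on ρ. These figures assume 40 completers, normal data and changes independent of baseline; the documents give none of the correlations.

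The affected items are secondary and exploratory in a pilot. The primary between-group comparisons and the planned correlation of steatosis reduction with weight and visceral fat loss are not affected.

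**What to change.** In 9.1.3 and 10.2:

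1. Add the correlation of change in liver stiffness with change in liver fat.
2. Replace the pairing of adrenal size and cortisol levels with weight change by change in adrenal size and change in cortisol (follow-up adjusted for baseline), each against weight change over the same interval.
3. Do both for baseline to month 2 (or end of ketosis, as 9.1.3 defines it) and baseline to month 6. Adjust for randomised arm by partial correlation or a regression with an arm term, and give 95% CIs.
4. Keep the level correlations, name baseline as their visit and label them cross-sectional.
5. If visits are pooled, use a model with a patient effect; 40 patients at three visits are not 120 independent points.
6. Align Section 4 with 5.2, 9.1.3 and 10.2.

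The cost is a few sentences and six exploratory coefficients (three pairs over two intervals), some of them replacing existing items. No further patients, scans or visits are needed. This assumes adrenal size is read from the same MRI at each visit, since the flow chart gives it no line of its own.

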9.2 Study procedures

9.2.1 *Follow-up of patients*

The patient follow-up will be 6 months. The patients will be visited monthly and data will be recorded on 4 occasions: pre-inclusion, baseline visit, final visit Active stage (end of ketosis) and visit at month 6.

Patients will be included after verifying the inclusion and exclusion criteria and after obtaining the signed informed consent.

Screening visit (day -15). In this visit, the patient's medical history will be assessed and a complete blood test will be required to verify the inclusion/exclusion criteria: complete blood count (red blood cells, leukocytes, neutrophils, hematocrit, hemoglobin), fasting blood glucose, Hb1c, insulinemia, lipid profile (total cholesterol, c-HDL, c-LDL, triglycerides), kidney function (serum creatinine, creatinine clearance, glomerular filtration), nitrogen balance (urea, uric acid), thyroid profile (TSH, T4) and ionogram (Na, K, Cl, Ca, Mg)

The pre-inclusion blood test will also include liver function tests as the first screening of hepatic steatosis:

- GOT
- GPT
- Gamma-GT
- Bilirubin
- Albumin
- Prothrombin time
- Ferritin
- Alkaline phosphatase.

In addition, the patients will be informed about the study through the patient information sheet (Attachment 1) and they will be provided with an informed consent (Attachment 2).

At the baseline visit (day 0). The results of the additional tests (blood tests) will be verified to complete the inclusion/exclusion criteria.

Liver function data will be reviewed. Patients with one or more of the following conditions will be considered as suspicious of hepatic steatosis:

- GPT/GOT ratio over 1
- Gamma-GT and alkaline phosphatase increased twice to three times the normal levels
- High ferritin
- Normal bilirubin and albumin in the presence of any of the above changes

The informed consent will be signed and randomized. The corresponding diet will be scheduled depending on the treatment group (VLCK diet group or control group) and the physical exercise program. Patient demographics (sex, age, weight, height, comorbidities and medication) will be recorded. Anthropometric data (weight, BMI, waist circumference) will be recorded. Fat infiltration into liver and visceral fat will be scanned by MRI and hepatic stiffness will be assessed by MR Elastography. The salivary cortisol levels will also be tested.

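### Adrenal size is the only secondary variable left out of the change analysis, and its planned correlation with weight change uses gland size rather than change in gland size, with no visit named

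*Combined protocol and SAP*

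**What the plan says.** Section 9.1.2 lists four secondary variables: liver stiffness, "Adrenal gland linear measurement", body weight and salivary cortisol. The secondary aim in 5.2 concerns a "linear correlation between adrenal gland size and variables commonly associated to insulin resistance", and names BMI, visceral fat and liver steatosis as those variables. The matching end point in 9.1.3 is "Correlation between adrenal gland size and BMI, visceral fat and liver steatosis".

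The Introduction (section 4) supplies the reasoning. The gland is larger in metabolic syndrome and, once treatment is under way, "leading to weight loss and diminished insulin resistance, the increase in adrenal volume tends to be reversible". The same section says that the linear adrenal measurements are made "to address its correlation with weight loss, visceral fat and liver steatosis".

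Section 10.2 has two parts. The first lists the changes to be compared between visits and between groups: liver fat, liver stiffness, salivary cortisol, weight, BMI, waist circumference and visceral fat. The second plans Pearson or Spearman correlations, among them "the association between adrenal gland size and salivary cortisol levels with weight changes, BMI, hepatic steatosis and visceral fat". The flow chart in 9.2.2 schedules MRI at onset, month 2 and month 6.

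**The concern.** Reversal with weight loss is a statement about change within a patient. The repeated MRI could show it, and random allocation to two diets would allow a comparison of adrenal change between arms. Section 10.2 asks for neither a paired nor a between-group test of adrenal change.

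The planned correlation does not clearly fill the gap. Gland size at one visit reflects mostly how large that person's adrenals are anyway, and only partly how they responded to the diet. Set against weight change, the response is mixed with stable differences between people. If the baseline measurement were used, the correlation could show no shrinkage at all, because none has yet occurred. At stake is a weak or null adrenal result even where the glands do shrink with weight loss, and a choice of visit and of size or change that would be made after the data are seen.

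**Working it through.** **1. Which secondary variables are in the change analysis?**

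| Secondary variable (9.1.2) | In the change list of 10.2? |
|---|---|
| Liver stiffness | Yes |
| Adrenal linear measurement | No |
| Body weight | Yes |
| Salivary cortisol | Yes |

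The adrenal measurement is the only one missing.

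**2. How is the adrenal correlation worded, compared with its neighbour?** For the liver, 10.2 relates a reduction in steatosis to weight loss and loss of visceral fat, which is change against change. For the adrenal, the same sentence relates gland size to weight changes. No visit is given. Read literally, this is a level against a change.

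**3. Is there a figure in the plan to reproduce?** No. Section 7.5 justifies 20 patients per group without an effect size, SD or power, and no adrenal SD appears anywhere.

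**4. How much could be lost? (illustration only)** Write follow-up size as L = S + D, where S is stable size and D is the adrenal change. Let W be the weight change. If S is unrelated to W, then

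corr(L, W) = corr(D, W) × SD(D) / SD(L).

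Assumptions, none from the documents: corr(D, W) = 0.50, with 0.30 as a lower alternative; SD(D)/SD(L) between 0.3 and 0.5; 40 complete patients; two-sided 0.05 (10.2 gives 0.05 but not the sidedness). Power is by Fisher z: the mean of the test statistic is atanh(r) × √(40 − 3), compared with 1.96 in both tails.

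| Change-v-change r | Power | Size-v-change r | Power |
|---|---|---|---|
| 0.50 | 91.6% | 0.50 × 0.3 = 0.15 | 15.1% |
| 0.50 | 91.6% | 0.50 × 0.5 = 0.25 | 34.2% |
| 0.30 | 46.9% | 0.30 × 0.3 = 0.09 | 8.5% |
| 0.30 | 46.9% | 0.30 × 0.5 = 0.15 | 15.1% |

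If the 30-50% is instead taken relative to SD(S), with S and D unrelated, then SD(L) = SD(S) × √(1 + k²), where k is the ratio. For r = 0.50 the diluted values become 0.15/√1.09 = 0.14 and 0.25/√1.25 = 0.22, with power of about 14% and 28%.

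For scale, the correlation detectable with 80% power at n = 40 is tanh((1.96 + 0.84)/√37) = 0.43.

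**5. What could an added change analysis detect?** At 80% power, two-sided 0.05, with complete data:

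- Between arms, 20 per arm: (1.96 + 0.84) × √(2/20) = 0.89 SD (0.91 with the t distribution).
- Within one arm, n = 20: (1.96 + 0.84)/√20 = 0.63 SD of the change (0.66 with t).
- Within patients, both arms pooled, n = 40: (1.96 + 0.84)/√40 = 0.44 SD of the change (0.45 with t).

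**The case against.** The strongest reply is that the plan does what the protocol asks. The stated hypothesis and the end point are correlations of adrenal size with BMI, visceral fat and steatosis, and 10.2 prespecifies exactly those. Reversal is background in the Introduction, not an aim or an end point. A reader might infer that the trial cannot test its adrenal hypothesis. The documents do not support that: the stated hypothesis is testable as planned, and the repeated scans would allow a change analysis even though none is written down. This part of the reply stands.

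It can also be said that gland size paired with weight changes may have been meant as change in gland size. That is possible, but the wording does not say so, and the liver correlation in the same sentence does name a reduction. Nor does the descriptive analysis in 10.1 help: it covers all collected variables with confidence intervals, but sets up no paired or between-group comparison of adrenal change.

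The power figures are fairly criticised. They rest on assumed inputs and concern only the correlation with weight change, not those with BMI, visceral fat and steatosis. They show direction and possible scale, nothing more.

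Two further inferences are tempting and should be resisted:

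- That the entry criteria leave too little spread for a cross-sectional correlation. BMI has no upper limit apart from the 140 kg weight limit, visceral and liver fat are unrestricted, and no variance is given.
- That insulin resistance itself must enter the adrenal analysis. The aim in 5.2 names BMI, visceral fat and steatosis as examples of its correlates. The panel with "fasting blood glucose, Hb1c, insulinemia, lipid profile" is specified in that detail only at screening; at months 2 and 6 section 9.2.1 asks for a complete blood test with liver function and does not name insulin.

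Finally, repeated adrenal measurement is itself an inference from the MRI schedule. No visit description in 9.2.1 names it.

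**Conclusion.** The omission is real and clear from the text. Adrenal size alone among the secondary variables has no between-visit or between-group comparison, and its correlation with weight change is written in terms of size, with no visit. For the purpose given in the Introduction, correlation with weight loss, change against change is the better analysis, and the plan does not specify it.

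The consequence is limited. It concerns one secondary aim of an exploratory pilot, leaves both primary variables untouched, and does not prevent a test of the stated correlation. The possible loss, from about 92% to about 15-34% power, is illustrative: it depends on an assumed true correlation of 0.50, an assumed SD ratio of 30-50%, stable gland size unrelated to weight change, a follow-up measurement and 40 complete patients. With an assumed correlation of 0.30, even change against change has only about 47% power. This is a cheap improvement to the analysis plan, not a failure of the design.

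**What to change.** 1. In 9.1.3, add change in adrenal linear measurement from baseline to month 2 (or end of ketosis) and from baseline to month 6.
2. In 10.2, add adrenal change to the changes compared between visits and between groups.
3. In 10.2, correlate adrenal change with change in weight, BMI, visceral fat and liver fat over the same interval.
4. Keep the baseline cross-sectional correlation of adrenal size with BMI, visceral fat and steatosis as the test of the stated hypothesis, and name the visit.
5. In 9.2.1, state that the adrenals are measured on each of the three scheduled MRIs.

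The cost is a few lines of text, the reading of the glands on scans already scheduled if that was not intended at every visit, and a little more analysis. There are three drawbacks. A change score carries the measurement error of two readings, which is one reason to keep the baseline correlation. The number of exploratory tests rises slightly. Between-arm power is modest: about 0.9 SD is needed for 80% power at 20 per arm, so the results should be reported as estimates with confidence intervals and labelled exploratory.
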